#### **Secondary outcome variable(s)**

Secondary outcomes of the study will include colonoscopy show rate, bowel preparation quality (rescue, poor, fair, adequate, good, excellent; we will also collect Boston Bowel Prep Score if available [scale 0-9]), colonoscopy cancellation rate, timing of advance cancellation notification (days), colonoscopy reschedule rate, and colonoscopy appointment no-show rate. A colonoscopy "show" will be defined as a patient who attends their originally scheduled colonoscopy appointment. A "cancellation" will be defined as an appointment that is canceled at least one day prior to the originally scheduled colonoscopy appointment date. A "reschedule" will be defined as an appointment that is canceled and rescheduled (for a future date) on the same day, at least one day prior to the originally scheduled colonoscopy appointment date. Finally, as an additional secondary outcome, we will also collect the proportion of patients who opt out of the texting program in the late phase of enrollment (described below).

Formatted: Font color: Black

#### **Background**

Colorectal cancer (CRC) is the second leading cause of cancer death in the US, yet there are effective screening and treatment strategies that allow for early detection and treatment. CRC screening is recommended for all individuals aged 50-75, which could include stool testing or colonoscopy, but national rates are still suboptimal at 59-65%. Colonoscopy is an essential component of CRC screening, as it is also required if stool testing is positive. However, colonoscopy requires a complex process to identify an escort, purchase the preparation, take a day off from work, adhere to a clear liquid diet, and complete the split-dose preparation as recommended. This results in a significant no-show and cancellation rate, along with suboptimal preparation quality, which can lead to non-adherence and incomplete screening.

Current approaches to engaging patients include having nurses call patients before the procedure or patient navigators. However, it is often difficult to get patients on the phone, and these interventions can be costly, making it less scalable for clinical practices. Other interventions such as videos or mobile apps have been limited by poor user experience or limited engagement with the patient. There is an opportunity to leverage an automated text message navigation intervention using the Way to Health (WTH) platform to improve patient engagement prior to colonoscopy completion. The WTH platform is a Penn Medicine platform that is hosted on site at the University of Pennsylvania. The platform allows custom text messages to automatically be sent to patients, in addition to bidirectional message capabilities. WTH is protected by a secure firewall and is a HIPAA compliant platform.

In the past year, our team conducted a quality improvement pilot initiative using WTH that tested the feasibility and impact of a one-week text messaging protocol for patients who were scheduled for outpatient colonoscopy. The text messages sent to patients contained information about the preparation process and instructions, expectations about the procedure, and reminders about location and timing. Among the 21 patients enrolled in the pilot, we found high user acceptability and higher

colonoscopy show rates as compared to baseline values at PPMC (90% versus ~50%). As such we believe that the texting intervention is feasible for testing in the context of a randomized controlled trial.

### Study Design

#### Design

We will perform a pragmatic randomized controlled trial evaluating the impact of the text message-based intervention (arm 2) as compared to usual care alone (arm 1). Patient enrollment will proceed through two pathways (early phase and late phase). In the early phase, 250 patients will be enrolled through, or through phone calls from a clinical research coordinator, using a script pre-approved by the University of Pennsylvania Institutional Review Board. After enrollment, patients will be randomized 1:1 to the arms listed above through the Way to Health platform. Although patients in arm 2 may be enrolled more than one week in advance of their colonoscopy, they will only receive intervention text messages in the 7 days prior to the scheduled colonoscopy, in addition to two text messages at the time of enrollment explaining the texting program. Usual care consists of a phone call from the PPMC endoscopy staff in the week prior to colonoscopy, if the patient is able to be reached. Patients are also given the endoscopy phone number, and may call to speak to staff if they have specific questions about their colonoscopy or need to reschedule. In the late phase, an additional 500 patients will be automatically enrolled in the Way to Health system using verified cell phone numbers from the electronic medical record system, where they will be randomized in a 1:1 ratio to the study arms in variable blocks of 8 and 4. Patients in arm 2 will receive two enrollment text messages explaining the texting program and providing the opportunity to opt out (by replying with the text STOP). A detailed outline of the study design can be found in the procedures sections.

**Deleted:** be performed with assistance from the call center at the Pennsylvania Presbyterian Medical Center (PPMC), and/

**Deleted:** s or months

#### Study duration

The duration of participation for patients in the intervention will be from the time of enrollment to the date of scheduled colonoscopy. However, the patient will only receive intervention text messages in the week prior to the scheduled colonoscopy, with the exception of the two enrollment messages in the late phase. We will plan to recruit patients from November 2018 through June 2019. We estimate that the study will be completed by August 2019.

**Deleted:** January

**Deleted:** March

#### Resources necessary for human research protection

Describe research staff and justify that the staff are adequate in number and qualifications to conduct the research. Describe how you will ensure that all staff assisting with the research are adequately informed about the protocol and their research related duties. Please allow adequate time for the researchers to conduct and complete the research. Please confirm that there are adequate facilities for the research.

The project will take place at the Pennsylvania Presbyterian Medical Center (PPMC) at the University of Pennsylvania (UPENN). The team includes investigators experienced in clinical medicine, health behavior interventions, clinical trials, behavioral economics, and program evaluation. This study will be led by [name], MD, MBA, MSHP, Assistant Professor of Medicine and Associate Chief Innovation Officer for Penn Medicine. This study will be supported on a secure web portal on the Way to Health platform, modified to the specifications of this study. Additional study staff include a gastroenterology fellow, a clinical research coordinator, a medical student, key PPMC endoscopy staff, and quality improvement specialists. Regular group meetings will be held at pivotal points in the trial in order to ensure compliance with protocol and research-related duties.

### Characteristics of the Study Population

#### Target population

Eligibility Criteria: Patients will be eligible for study inclusion if they are age 18-85 years and are scheduled for outpatient colonoscopy to be completed at the PPMC outpatient endoscopy center. We will exclude patients if there are fewer than 14 days from time of scheduling to the scheduled date of colonoscopy. The target enrollment sample size is 750 patients—375 in arm 1 (usual care) and 375 in arm 2 (usual care plus texting intervention). This number is based in part on sample size calculations using data from a previous pilot, which suggests that a total sample size of 750 patients will have greater than 80% power to detect a 10% difference in the primary outcome. We also chose a larger sample size to account for the fact that patients may opt out of the text messages in the late phase of enrollment, which would likely decrease the effect size between arms.

#### Subjects enrolled by Penn Researchers

750

Deleted: 0  
Deleted: 40  
Deleted: 2  
Deleted: 00  
Deleted: 2  
Deleted: 00  
Deleted: 20  
Deleted: 5  
Deleted: .  
Deleted: 40

#### Subjects enrolled by Collaborating Researchers

0

### Accrual

Participants in the study will be planned for outpatient colonoscopy at the Pennsylvania Presbyterian Medical Center (PPMC). Once a patient is confirmed to meet eligibility criteria, patient enrollment will proceed based on one of two pathways (early and late phase). In the early phase (first 250 patients), enrollment will be performed through phone calls from a clinical research coordinator. The research coordinator will call newly scheduled patients to discuss the research project and enroll patients using a script to be approved by the University of Pennsylvania IRB. If patients are scheduled for colonoscopy in person while at the office, they will receive an informational flyer about the study that gives them the opportunity to contact a study team member for additional information or to enroll. It also informs

Deleted: be performed  
Deleted: with assistance from the call center at PPMC, and/or  
Deleted: When patients have a physician order for a colonoscopy, the patient must contact the call center in order to schedule the colonoscopy. The call center staff have agreed to discuss the research project and enroll patients using a script to be approved by the IRB. Similarly, Deleted: be

them that someone from the study may contact them directly about participating. After enrollment, patients will be 1:1 randomized to arm 1 or arm 2 using the Way to Health platform.

Moved (insertion) [1]

In the late phase (additional 500 patients), patients with upcoming colonoscopy appointments will be screened for eligibility as per the selection criteria. As in the early phase, if patients are scheduled for colonoscopy in person while at the office, they will receive an informational flyer about the study that lets them know they may be contacted by text message about their upcoming procedure. Those who qualify will have their validated cell phone numbers imported into Way to Health, where they will subsequently be randomized. Those in the intervention arm will receive two enrollment messages describing the study and providing the opportunity to opt out (by replying with the text STOP). Of note, if a patient in the late phases chooses to opt out and not receive the texting intervention, their data will still be analyzed in the intervention group (as an intention-to-treat approach). Importantly, we are

requesting a waiver of consent for several reasons: (1) the study presents no more than minimal risk of harm to participants, (2) the patients who are randomized to either arm will not be deprived of any standard care available in the status quo and thus the study will not violate their rights or welfare, (3) the study could not be practicably completed without such a waiver, as the scheduling process is handled over the phone by call center staff, and (4) requiring standard informed consent would require an additional touchpoint by the research coordinator and the consent process would preclude us from evaluating the intended intervention by introducing selection bias and altering the intervention that patients receive.

Moved up [1]: After enrollment, patients will be 1:1 randomized to arm 1 or arm 2 using the Way to Health platform.

#### Key inclusion criteria

Eligibility Criteria: Patients between ages 18 and 85 years who are scheduled for outpatient colonoscopy at PPMC and have a cell phone with enabled text messaging capability.

#### Key exclusion criteria

Exclusion Criteria: Patients will be excluded if there are fewer than 14 days between the time of enrollment and time of scheduled colonoscopy. This will ensure the clinical research coordinator has sufficient time to reach newly scheduled patients, and that patients randomized to arm 2 will have sufficient time to receive the full text message intervention. Patients will also be excluded if they are non-English speaking requiring a translator, or if they are not the primary individual receiving the text messages. Finally, patients will be excluded if they do not meet all of the inclusion criteria, or if they refuse participation in text messaging.

Deleted: 0

## Procedures

Screening – Phase 1: As above, patients will be screened and enrolled through one of two pathways (early and late phase). In the early phase (first 250 patients), a PPMC practice manager will forward a list of scheduled colonoscopies to the clinical research coordinator (CRC) on a regular basis. If patients are scheduled for colonoscopy in person while at the office, they will receive an informational flyer about the study that gives them the opportunity to contact a study team member for additional information or to enroll. It also informs them that someone from the study may contact them directly about participating. The CRC will screen patients for eligibility and make up to 3 phone call attempts to reach the patient. Once on the phone, the CRC will explain the details of the study using a script approved by the IRB and enter patients directly into the WTH platform for randomization. In the late phase (additional 500 patients), patients will be screened for eligibility through the same process as in the early phase. If they are scheduled for colonoscopy in person while at the office, they will also receive an informational flyer about the study that lets them know they may be contacted by text message about their upcoming procedure. For eligible patients, the CRC will then manually enter the validated patient cell phone number from the electronic medical record system into WTH. Randomization will then occur as described below, and intervention arm patients will receive two enrollment messages. These messages will describe the texting program and provide the opportunity for patients to opt out (by texting the word STOP). Of note, phone numbers will be confirmed to represent cell phones by using a publicly-available lookup utility. Importantly, patients who opt out will still be included in the intervention arm as an intention-to-treat analysis. Based on our experience with the QI pilot described above, we estimate needing to screen approximately 1,000 patients to meet our enrollment targets (750 total patients).

**Deleted:** Patients who have a physician order for a colonoscopy will call the PPMC call center in order to schedule their procedure. At this time, the call center staff will screen the patient for eligibility (age criteria and text messaging ability) and will explain the details of the study following a pre-determined script. Patients who agree to participate in the study will have their cell phone number recorded. A list of these patients will be forwarded to the clinical research coordinator on a weekly regular basis, who will confirm patient eligibility and then manually enter patients into the WTH platform for randomization. Alternatively,

**Deleted:** for

Randomization - Phase 2: In the early phase, using a random number generator in the WTH platform, patients will be 1:1 randomized to arm 1 or arm 2. Beginning in the late phase of enrollment, patients will be randomized to arm 1 or arm 2 in a 1:1 ratio in variable blocks of 8 and 4 using the WTH platform, until the target sample size of 375 patients per arm is reached.

**Deleted:** between 500 and

**Deleted:** 6

**Deleted:** 40

**Deleted:** , until the target

**Deleted:** sample size of 200 patients per arm is reached. Randomization will be performed and recorded in WTH.

Chart review - Phase 3: after randomization and in tandem with phase 4 (below), the research coordinator will perform a chart review to obtain patient demographic and comorbidity data (hypertension, hyperlipidemia, diabetes, inflammatory bowel disease, obesity, active opiate prescription). We will also collect data on the number of patients opting out in the late phase of enrollment, as well as data on nursing phone calls which are performed as a component of usual care (not called, called but could not reach patient, called and spoke with patient). All data will be inputted into and stored in a secured RedCap database. Only key study staff will have access to the RedCap database, which is stored on a secure firewall-protected server.

Intervention - Phase 4: Patients in arm 2 will begin receiving text messages per a pre-determined protocol starting 7 days prior to the date of scheduled colonoscopy (the text messaging protocol is attached to this application). Of note, if a patient in arm 2 cancels or reschedules their colonoscopy after randomization, they will not receive any additional protocol text messages as part of this trial. Patients in arm 1 and arm 2 will both receive usual care, which includes (1) bowel preparation instructions that are delivered via mail or through a secure online messaging portal, (2) a phone call from the endoscopy

staff in the week prior to colonoscopy, and (3) the option to call the endoscopy staff during business hours to have any questions answered on demand.

Outcomes data collection - Phase 5: After a patient's scheduled colonoscopy date has passed, the research coordinator will review the medical record to gather additional data from the endoscopy procedure. This will include the indication for the procedure, quality of bowel preparation (rescue, poor, fair, adequate, good, excellent; Boston Bowel Prep Score will also be collected if recorded), and completeness (cecum reached). Procedure status will also be recorded (canceled, no-show, rescheduled, completed). If the procedure was canceled, the cancellation lead time (in days) prior to scheduled colonoscopy will be recorded.

Statistical Analysis and Manuscript Preparation - Phase 6: The statistical analysis (detailed below) will commence after completion of outcomes ascertainment for the entire cohort.

#### **Analysis Plan**

Descriptive analysis will include comparison of baseline demographics and major medical comorbidities between study arms. Continuous and categorical data will be compared using the Wilcoxon Rank-sum and Chi-squared tests, respectively. An alpha threshold of 0.05 will be used for statistical significance, with two-tailed testing performed in all instances. For the primary analysis, we will perform a Chi-squared test of independence to compare the proportion of colonoscopies with good/excellent bowel preparation between groups. In the secondary analysis, Chi-squared tests of independence will be performed to compare colonoscopy status (show, no-show, reschedule, cancellation) as well as bowel preparation quality (excellent, good, adequate, fair, poor) between groups. Among canceled colonoscopies, median lead time of cancellation will be compared between groups using the Wilcoxon Rank-sum test. Finally, for both primary and secondary analyses, we will consider multivariable regression modeling to adjust for imbalances in possible confounders, if present despite randomization.

**Deleted:** Finally, a

#### **Consent**

##### **1. Consent Process**

###### **Overview**

We are requesting a waiver of informed consent for this study. The reason for our request is explained in the Waiver of Consent section. Verbal consent for text messaging will still be obtained from all participants in the study. Please see the script templates attached to this application.

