###### **Adult Subjects Not Competent to Give Consent**

We are requesting a waiver of informed consent for this study but patients will still need to verbally opt in to text messaging. We plan to enroll only those patients who are competent at time of enrollment to opt-in for themselves.

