#### **Impact on Subject Rights and Welfare\***

Participation in the intervention is completely voluntary and subject rights and welfare will not be adversely affected by the waiver of authorization and consent. Participants randomized to the intervention arms still need to opt in to text messaging: Arm 1 will receive standard clinical care and Arm 2 will be enrolled into the text-messaging program in addition to standard clinical care. Placement in either arm for the purposes of research does not adversely affect the rights and welfare of the subjects, as each arm has the opportunity to engage in colorectal cancer screening, receive bowel preparation instructions, and communicate with the endoscopy staff over the phone. Randomly assigning patients to intervention and control does not alter patient's rights any differently than conducting an uncontrolled pilot study where some patients receive the intervention and some don't. We believe it is appropriate to obtain waiver of consent because learning the impact of different modalities for improving colorectal screening has significant potential clinical value for the practice (i.e. significantly increasing the rate of successful screening and thus decreasing the rate of mortality related to nonuse of screening).

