#### **Waiver Essential to Research\***

The informed consent process itself may influence the outcome of our study, as it would require an additional phone call by the research coordinate to ask for participation. The purpose of the Way to Health text messaging program is to provide timely reminders regarding colonoscopy preparation. Obtaining waiver of consent would allow us to avoid the potential selection/volunteer bias for inclusion of patients who answer the phone and may be particularly motivated to complete colon cancer

screening. Since our main objective is to understand the potential influence of the text messaging intervention on colonoscopy show rate and adequate bowel preparation quality among all patients who agree to text messaging, we believe that obtaining informed consent separately from scheduling would not allow us to evaluate the impact of the intended intervention, which is text messaging navigation offered to all patients that agree during scheduling. Additionally, participants will be recruited via verbal communication when they call our institution call center to schedule their colonoscopy. We believe the research presents no more than minimal risk of harm to subjects and involves no procedures for which written consent is normally required outside of the research context.

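### The final protocol says all participants give verbal consent to texting, but the late phase enrolls 500 of 750 patients without it, so the consent, exclusion and population statements need reconciling

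*Combined protocol and SAP*

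**What the plan says.** All references are to the final protocol unless stated.

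**Consent sections.** The Consent Process overview requests a waiver of informed consent but adds: "Verbal consent for text messaging will still be obtained from all participants in the study". The section on adults not competent to consent says "patients will still need to verbally opt in to text messaging" and limits enrollment to people able to opt in for themselves. The section on subject rights and welfare says: "Participants randomized to the intervention arms still need to opt in to text messaging".

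**Waiver section (Waiver Essential to Research).** The main objective is described as the effect on show rate and preparation quality "among all patients who agree to text messaging". On recruitment it says: "participants will be recruited via verbal communication when they call our institution call center to schedule their colonoscopy".

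**Design, Accrual and Procedures.** Enrollment has two phases. The first 250 patients are enrolled through calls from a research coordinator. Then "an additional 500 patients will be automatically enrolled in the Way to Health system using verified cell phone numbers" taken from the medical record. These patients are randomized first. Only those allocated to arm 2 then receive two messages, which explain the program and let them leave by texting STOP. Accrual and Procedures both say that patients who opt out stay in arm 2 for an intention-to-treat analysis.

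**Key exclusion criteria.** Refusing to take part in text messaging is an exclusion.

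**Overall objectives.** The aim is to evaluate the texting intervention. It is not restricted to patients who agree.

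**The concern.** The consent sections and the enrollment sections give different rules for the same patients, and no consent passage is limited to the early phase. Both cannot be followed in the late phase. Applied literally, the verbal rule would confine the late phase to patients who were reached and agreed, which changes who is enrolled. Under the enrollment procedure, the consent statement is untrue for most participants.

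Two statistical matters follow. First, the population is described in two ways: unrestricted under Overall objectives, and limited to agreeing patients in the waiver section. Second, the exclusion for refusing texting works before randomization in the early phase. In the late phase, refusal becomes visible only after randomization and only in arm 2.

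**Working it through.** This is a consistency check, so the only arithmetic is a count.

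**Inputs.** Early phase: 250 (Design, Accrual, Procedures). Late phase: 500 (same sections). Total: "The target enrollment sample size is 750 patients", with 375 per arm (Target population and final SAP). Allocation: 1:1 in both phases (Procedures, Randomization).

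**Reproducing the plan's total.** 250 + 500 = 750, which agrees with the stated target.

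**Share without a verbal step.** 500 / 750 = 66.7%.

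**Split by arm.** At 1:1, 500 / 2 = about 250 late-phase patients per arm. About 250 in arm 2 have only an opt-out, offered after allocation. About 250 in arm 1, or 250 / 750 = 33.3% of the trial, receive no study text at all.

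**Statements compared with each phase.**

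| Statement | Early phase (250) | Late phase (500) |
|---|---|---|
| Verbal consent from everyone (Consent Process overview) | Compatible with the coordinator call | Not met; no call is made |
| Verbal opt-in, by patients competent to give it (section on adults not competent) | Compatible | Not met; enrollment comes from the record |
| Arm 2 participants must opt in (subject rights and welfare) | Compatible | Replaced by opt-out |
| Recruitment by call center (waiver section) | Not met; coordinator calls | Not met; no call |
| Objective among patients who agree (waiver section) | Matches who is randomized | Agreement unknown at randomization |
| Exclusion for refusing texting (Key exclusion criteria) | Applied before randomization | Visible only in arm 2, after randomization |

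**The exclusion.** If a STOP reply were treated as an exclusion, refusers would leave arm 2 while comparable patients stayed in arm 1, and the arms would no longer be comparable. Accrual and Procedures direct the opposite by keeping these patients in arm 2. The exclusion criterion does not say so.

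**Phase in the analysis.** Recruitment differs by phase, and so does randomization: a random number generator early, variable blocks of 8 and 4 late. The Analysis Plan and the final SAP specify an unstratified chi-squared test and no result by phase.

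**The case against.** **The enrollment text is clear.** Design, Accrual and Procedures are detailed and agree with one another about the late phase, while the consent sections repeat the initial protocol's wording. Staff have one workable procedure. This stands, and it keeps the practical risk low, but it does not make the consent statement true.

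**A waiver is requested, and patients are informed.** The overview says verbal consent is obtained despite the waiver, so the waiver does not settle the matter. The flyer reaches only patients scheduled in person, and in the late phase it tells them they may be texted without asking for agreement. The STOP option is real, but it comes after randomization and only in arm 2.

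**Stronger readings that the documents do not support.**

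- A reader might infer that following the verbal-consent rule would leave no opt-outs after randomization. The section on additional information to subjects lets intervention participants stop at any time.
- A reader might infer that the trial does not answer its stated objective. The Overall objectives and the Abstract do not restrict the aim to agreeing patients; the restriction appears in the waiver justification. The conflict is between those two descriptions.
- A reader might infer a specific loss of power. The documents give neither an opt-out rate nor a control rate for the primary outcome. Dilution would arise from opt-out enrollment with intention-to-treat analysis however the consent text was worded. Target population and the final SAP cite opt-outs as a reason for the larger sample, and the opt-out proportion is a secondary outcome.
- A reader might infer that pooling the phases is invalid. Allocation is 1:1 in both, so phase is not expected to confound the comparison.

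**Conclusion.** The contradiction lies within the current final protocol. The verbal consent rule does not fit the enrollment method of 500 of 750 patients (67%), a share that comes directly from the protocol's targets and rests on no outside assumption. The call-center sentence fits neither phase. The refusal exclusion needs a qualification for the late phase, and the waiver section's population differs from that of the Overall objectives.

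The plan should be amended on this point, but it is not a fault in the randomized comparison. The pooled intention-to-treat contrast and the unstratified test remain valid. What has to be settled is the consent rule for the late phase and the population the pooled estimate describes: it combines patients who agreed before randomization with patients whose agreement was not sought before it.

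**What to change.** 1. Reconcile the Consent Process overview, the section on adults not competent to consent, the subject rights and welfare section, the waiver section and Key exclusion criteria with Overall objectives, Design, Accrual and Procedures. Have the IRB confirm the result.
2. State which phase has verbal agreement and which has a waiver with opt-out, and correct the call-center sentence.
3. State that a STOP reply in the late phase is not an exclusion, in line with the intention-to-treat rule already given.
4. State one population for the pooled intention-to-treat estimate, and use it in both the objectives and the waiver section.
5. As an improvement rather than a correction, stratify the primary comparison by enrollment phase, for example with a Mantel-Haenszel test, and report the risk difference in each phase descriptively.

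The cost is amendment wording, IRB confirmation and one stratification factor, with no extra patients or procedures. The pooled result could not be described as applying only to patients who agreed to texting.
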